## 12 Statistical considerations

#### 12.1 Power analysis

Power analysis for error rates and reaction times is based on effect sizes from previous studies of the Emotional Go/NoGo task in subjects with schizophrenia and our preliminary data from a secondary analysis of a clinical trial of the alpha-7 nicotinic agonist GTS-21. With a sample size of 25 subjects, we will achieve 80% power at  $\Box$ lpha = 0.05 to detect a difference from 35% to 10% in the omission error between two experimental conditions within a subject (expected correlation of 0.60) and to detect an effect size of 0.6 in the mean reaction times between the control and intervention conditions within a person using paired t-test at alpha = 0.05. The dropout rate in a similar published acute crossover study of schizophrenia patients was ~15%. We thus anticipate needing to enroll 30 subjects to result in 25 completers for an appropriately powered study. We will match this group with a healthy control sample of similar size.

#### 12.2 Data analysis plan

Omission error rate will be analyzed using non-linear mixed effects modeling of a binary outcome omission error (0/1), while reaction time will be analyzed with a linear mixed effects model. In both models, there will be a random effect for subject, a primary fixed independent predictor treatment condition (nicotine or placebo), an independent adjustment variable block valence (emotional vs. non-emotional task), and the interaction of the latter two predictors to examine whether the omission error rate or reaction time between two treatment conditions is moderated by the valence. Significance will be established at alpha = 0.05.

We expect nicotine will reduce error rates in control blocks consistent with previous reports of improved attention with acute dosing of transdermal nicotine. We expect to find an interaction between valence and treatment such that performance improves with nicotine to a significantly greater extent in negative valence blocks. We further expect this increase to be more prominent in individuals with schizophrenia than in healthy controls. We expect salivary nicotine concentration, which is proportional to serum nicotine, will correlate with improvement in response inhibition. Based on previous findings in the Emotional Go/NoGo task, we do not expect to find an effect of antipsychotic exposure, as measured by chlorpromazine equivalents.

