#### 6.2 Testing: days 1 and 2

Testing occurs on two days separated by approximately one week, but no sooner than 5 days apart (Figure 1) to facilitate drug washout. Subjects will report to the Vanderbilt

Psychiatric Hospital. Female subjects will be administered a point of care urine pregnancy test to confirm absence of pregnancy. Subjects will have affixed to their skin a 7 mg nicotine patch or identical appearing placebo, covered by surgical tape so that neither the

subject nor the investigator can determine the identity. Previous studies of serum nicotine concentration suggests two hours post-patch application represents an approximate time of peak serum concentration in most subjects and is consistent with previously published protocols. Subjects will begin the behavioral task accompanied by EEG monitoring *at the latest* 120 minutes after patch placement, and will complete the task approximately 12 minutes later. At they time they will provide a saliva sample. This sample will be affixed solely with a non-identifiable code, frozen, and shipped to [name], University of Florida, for analysis of salivary nicotine which has been shown to correlate with serum nicotine levels and eliminates the need for venipuncture. The patch will then be removed.

interval. E, emotional block; NE, non-emotional block.

As noted above, up to two hours after nicotine or placebo patch placement, subjects will begin participation in an Emotional Go/NoGo task, based on the procedure described by Egashira et al, which compared medicated subjects with schizophrenia to healthy subjects and found the patient group was significantly more affected by negative emotional valence than were healthy controls despite only modest group differences with neutral valence stimuli. Subjects will also undergo electroencephalography during performance of the behavioral task. Fearful, sad, angry, and disgust faces (negative valence) and neutral faces will be taken from UPenn's publicly available PERT-96 color emotional stimuli bank. The entire task takes ~12 mins, including breaks, and is

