performed in 5 blocks of 32 trials, with 3 emotional blocks with angry/fearful/sad/disgust faces and 2 non-emotional blocks (Figure 1). Each stimulus is presented for 1 s with a 1 s interstimulus interval. In each block the subject is instructed on the go/no-go targets, each comprising 50% of the task stimuli, with instructions changing at the halfway point in each block. Each block contains two instructions. For example: Emotional blocks: go-angry/nogo-fear or go-fear/nogo-angry; Non-emotional blocks: go-male/nogo-female or go-female/nogo-male (Figure 2). Error rates and reaction times are recorded.

Figure 2 Emotional Go/NoGo schematic. Subjects are given a target instruction at the start of each block for 6 seconds. There is 1 second of blank screen between each 1 second stimulus presentation. In this schematic, the subject would press a key ("Go") when presented with the first stimulus (angry; green border represents the correct response is "Go". This border would not be present in the actual task), and withhold pressing a key for the second stimulus (sad; red border).

Subjects will be monitored for at least 30 minutes after patch removal to confirm the absence of side effects that would compromise their safety upon leaving the hospital.

Subjects will return for day 2 of testing not less than 5 days following day 1. On day 2, subjects will receive the treatment they did not receive on day 1. They will be asked a series of standard questions to assess for the presence of any side effects following their initial study day. If female, they will again be administered a urine pregnancy test to confirm the absence of pregnancy. The remainder of the procedure will be identical to day 1.

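### Both models in section 12.2 carry only a subject random effect, so session-to-session variation is left out of the nicotine effect's standard error and its false-positive rate exceeds 5%, by an amount the documents do not fix

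*Combined protocol and SAP*

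**What the plan says.** Section 12.2 of the combined protocol and SAP gives the same random part for errors and for reaction time: "In both models, there will be a random effect for subject, a primary fixed independent predictor treatment condition (nicotine or placebo"). Block valence and the treatment-by-valence interaction are the other fixed terms. No session term, subject-specific treatment slope or robust standard error is named. On the data level for errors it says: "Omission error rate will be analyzed using non-linear mixed effects modeling of a binary outcome omission error (0/1"), which reads as one record per trial. The level for reaction time is not stated.

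The design is in section 6.2. "Testing occurs on two days separated by approximately one week, but no sooner than 5 days apart", and "On day 2, subjects will receive the treatment they did not receive on day 1". The task is "performed in 5 blocks of 32 trials, with 3 emotional blocks" and 2 non-emotional ones. Go and no-go targets are described as "each comprising 50% of the task stimuli".

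Section 12.1 sizes the trial on within-subject pairs. For reaction time it refers to the difference between conditions "within a person using paired t-test at alpha = 0.05".

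**The concern.** Treatment is given to a session, not to a trial. With one session per treatment per subject, the treatment contrast in each subject is a difference between two days. Anything that shifts a whole session goes straight into that difference, for example sleep, fatigue, practice, nicotine exposure at testing or individual sensitivity to nicotine. A subject intercept removes what is common to both days. It does not represent what differs between them. The standard error then reflects only trial-level noise averaged over 80 trials, and is too small if sessions vary at all.

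Section 12.2 makes treatment the primary predictor and predicts fewer errors under nicotine in control blocks. That is a treatment effect within one valence, so it is also exposed. The p-values and confidence intervals for these effects would be too optimistic. The paired test used for sizing in 12.1 does carry session variation, so the analysis does not match its own sizing.

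**Working it through.** **Inputs from the documents.** 25 completers; alpha 0.05 (two-sided assumed, as sidedness is not stated); omission rates 35% and 10%; correlation 0.60; reaction-time effect size 0.6. Trials per session: 5 x 32 = 160, half of them Go, so 80 Go trials: 3 x 16 = 48 emotional and 2 x 16 = 32 non-emotional.

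**Assumptions.** The documents give no session, subject or trial SDs. All SDs below are assumed and varied. The subject random effect is read as an intercept.

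**Step 1: the plan's own figure.** A paired t-test at effect size 0.6 has 82.1% power with 25 subjects and 80.4% with 24. Dropout: 25 / 0.85 = 29.4, so 30 enrolled. Both agree with 12.1. This calculation uses the SD of paired differences, which includes session variation.

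**Step 2: closed form.** With n subjects and m trials per session, the true variance of the treatment effect is 2(s_session² + s_trial²/m)/n. The subject-intercept model reports about 2(s_trial²/m)/n. The ratio is

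R = 1 + m x s_session² / s_trial²

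and the false-positive rate is P(|Z| > 1.96/√R). The n cancels, so a larger sample does not reduce the excess.

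*Reaction time*, 70 correct Go trials, trial SD 150 ms, session SD 20 ms: R = 1 + 70 x 400/22,500 = 2.24; 1.96/1.50 = 1.31; rate about 19%.

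*Omission errors*, mean 22.5% (midpoint of 35% and 10%): the information per trial is 0.225 x 0.775 = 0.174, so 80 trials give 13.95. At session logit SD 0.3: R = 1 + 13.95 x 0.09 = 2.26; 1.96/1.50 = 1.30; rate about 19%.

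**Step 3: simulation with no nicotine effect.** Omission errors: logistic mixed models with a subject intercept, 25 subjects, subject logit SD 0.33 to 0.9, 4,000 runs per setting.

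| Effect tested | Session SD 0 | 0.2 | 0.3 | 0.5 |
|---|---|---|---|---|
| Treatment, averaged over valence | 5% | 10-12% | 18-19% | 33-35% |
| Treatment, emotional blocks | 5% | 9-10% | 14% | 27-28% |
| Treatment, non-emotional blocks | 5-6% | 7% | 10-11% | 19-20% |

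For the averaged effect, a mean error of 10% gives 8% and 13% at session SD 0.2 and 0.3; a mean error of 35% gives 12% and 20%. With 50 subjects the rates are 11%, 18% and 34% at 0.2, 0.3 and 0.5.

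Reaction time: 70 correct Go trials, trial SD 120-180 ms, 20,000 runs.

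| Data level | Session SD 10 ms | 20 ms | 30 ms |
|---|---|---|---|
| Single trials | 8-11% | 15-25% | 25-39% |
| Four cell means per subject | 7-8% | 10-14% | 14-18% |

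**Step 4: the interaction.** A session effect common to both valences cancels from the treatment-by-valence contrast. Its rate was 4-6%. It rose to 8-9% when session effects were allowed to differ by valence with SD 0.2.

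**Step 5: does the 0.60 correlation settle the size?** No. A session correlation of 0.59 arises with subject SD 0.33 and no session variation (rate 4.9%). It also arises with subject SD 0.6, session SD 0.3 and mean error 10% (rate 13.1%).

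**Step 6: remedies.** On the same simulated omission data, a session intercept tested against t with 24 df gave 3.3-5.8%, and a paired t-test on session summaries gave 4.2-5.9%. For reaction time the paired test gave 4.7-5.2%. In the session-by-valence setting, a session intercept alone left the interaction at 8.3-8.8%, while the paired difference of differences gave 5.2-5.5%.

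**The case against.** - **The random part may be under-described rather than wrong.** A subject-specific treatment slope would cure the problem, and the text does not say intercept only. But no slope is written, and an analyst following 12.2 would fit an intercept.
- **Every SD is assumed, and at zero session variance the rate is 5%.** This stands. The figures show a mechanism and a range. They do not measure this trial. Against that, the test is valid only if session variance is zero, which the plan does not argue.
- **The central hypothesis is the contrast of negative with neutral cues, which is largely untouched.** This also stands, and the claim is limited accordingly. Treatment is still the named primary predictor, and the control-block prediction in 12.2 is a treatment effect within one valence.
- **The salivary prediction proves little.** The plan writes "We expect salivary nicotine concentration, which is proportional to serum nicotine", and expects it to track improvement, which implies that response differs between subjects. If nicotine did nothing in anyone, there would be no such differences to omit. That is fair under that strict null. The prediction still bears on confidence intervals and on a null of zero average effect, and day-to-day variation does not depend on it.
- **Reaction time may be analysed on cell means.** The excess shrinks but remains. One value per session would remove it but could not hold the valence terms.

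**Conclusion.** The concern holds. As written, the 12.2 models leave nearly all session variance out of the standard error of the nicotine effect, whether averaged over valence or within one valence. The false-positive rate is above 5% whenever session variance is above zero. Over the assumed values it runs from 7% to 35% for omission errors at a mean error of 22.5%, and from 7% to 39% for reaction time. The direction follows from the design. The size does not, because the documents give no session variance. The conclusion rests on reading the subject effect as an intercept and omission errors as trial-level records. It does not extend to bias in the estimate, since order is randomised. It reaches the interaction test only if session effects differ by valence.

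**What to change.** In 12.2, replace the sentence on the random part with: *Both models will include random intercepts for subject and for session within subject.* With one session per treatment, this term covers both day-to-day change and individual response.

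Also state:
- that the session term is kept even if its variance is estimated as zero;
- whether the treatment test is averaged over valence or made within one valence;
- the reference distribution: t with subjects minus 1 df for errors, and Satterthwaite or Kenward-Roger df for reaction time;
- for the interaction, a subject-by-session-by-valence term where it can be estimated, because the session intercept alone does not protect that test;
- a fallback if a model fails: a paired analysis of one summary per subject per session, and the paired difference of differences for the interaction.

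The cost is a short text change and no new data. Confidence intervals will be wider, convergence may occasionally fail, and the test is slightly conservative (3-5%) if there is no session variation.

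### With only a subject random effect, the treatment-by-valence test in 12.2 can be declared significant too often if block effects differ between a subject's two sessions; a session effect does not cure this.

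*Combined protocol and SAP*

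**What the plan says.** Section 12.2 plans "non-linear mixed effects modeling of a binary outcome omission error (0/1") for omissions, "while reaction time will be analyzed with a linear mixed effects model". The first is explicitly trial-level. For reaction time the unit (trial, block mean or condition mean) is not given.

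On random effects the section says "In both models, there will be a random effect for subject" and stops there: no session, block or subject-by-condition term. The fixed effects are treatment, "an independent adjustment variable block valence (emotional vs. non-emotional task"), plus the product of those two, which serves as the test of whether valence changes the nicotine effect. The expected finding is that "performance improves with nicotine to a significantly greater extent in negative valence blocks".

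Section 6.2 describes the task as "performed in 5 blocks of 32 trials, with 3 emotional blocks with angry/fearful/sad/disgust faces and 2 non-emotional blocks". It adds that the Go/NoGo rule switches within a block, "with instructions changing at the halfway point in each block". Half the stimuli are Go targets. Each subject does the task twice, once on nicotine and once on placebo, at least 5 days apart.

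**The concern.** Valence does not vary within a block. Go trials in one block share the subject's state at that moment, the emotion pair and the current rule. A trial-level model with only a subject effect treats them as independent once the subject is known. If blocks fluctuate from one day to the other, the interaction is then tested against an error term that is too small.

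The interaction matters because section 2 states the hypothesis as an effect under negative cues compared with neutral ones. Section 12.2 also expects nicotine to reduce errors in the control blocks through better attention. The interaction is what separates a valence-specific effect from that general one, so a false positive here would support the trial's distinctive conclusion.

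**Working it through.** **The plan's own figures.** For a two-sided paired t-test with effect size 0.6, 24 subjects give 80.4% power and 25 give 82.1%. With 15% dropout, 25/0.85 = 29.4, so 30 enrolled. The sample size in 12.1 reproduces, and this point does not touch it. The documents give no power or type I figure for the interaction.

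**Inputs from 6.2 and 12.1.** 25 completers; 2 sessions; 3 emotional and 2 non-emotional blocks per session; m = 32 × 50% = 16 Go trials per block. Alpha is 0.05 (12.2), taken as two-sided.

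**Assumed, because the documents give no values.** Trial SD 150 ms (σ² = 22,500); block SD 20, 30 or 40 ms, with block variance split into a day-specific part d and a part s that repeats on both days.

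**Variance of the interaction.** For each subject let D = (nicotine minus placebo in emotional blocks) minus (the same in non-emotional blocks).

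- The subject effect cancels. A session effect enters the emotional and non-emotional means of that session equally, so it cancels too.
- A block effect that repeats on both days cancels in nicotine minus placebo.
- What remains is Var(D) = 2 × (1/3 + 1/2) × (d + σ²/m) = (5/3)(d + σ²/m). A subject-by-treatment-by-valence variance τ² in each of the four cells would add 4τ².
- The subject-only model sees a residual variance of about σ² + d + s and uses (5/3)(σ² + d + s)/m.
- With τ² = 0, the ratio of true to assumed variance is R = (σ² + m·d)/(σ² + d + s), and type I error = 2 × [1 − Φ(1.96/√R)].

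Worked case, block SD 30 ms (variance 900):

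- All day-specific: R = (22,500 + 14,400)/23,400 = 1.577; 1.96/1.256 = 1.561; type I error 11.9%.
- Half repeating: R = (22,500 + 7,200)/23,400 = 1.269; 1.96/1.127 = 1.740; 8.2%.
- All repeating: R = 22,500/23,400 = 0.962; 1.96/0.981 = 1.999; 4.6%.

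The same formula for all three SDs, beside a simulation with no treatment effect (25 subjects, 16 Go trials per block):

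| Block SD (share of variance) | All day-specific: formula / simulated | Half repeating: formula / simulated | All repeating: formula |
|---|---|---|---|
| 20 ms (0.017) | 8.1% / 7.8% | 6.4% / 5.6% | 4.8% |
| 30 ms (0.038) | 11.9% / 12.0% | 8.2% / 8.0% | 4.6% |
| 40 ms (0.066) | 16.5% / 16.9% | 10.5% / 10.6% | 4.3% |

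With all block variance repeating, the simulation gave 4.2 to 5.4%. A one-sample t-test on D stayed at 4.3 to 5.9% in every setting.

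**Omission error.** Logistic mixed models were simulated with 25 subjects, 22% omissions, session SD 0.5 on the logit scale and all block variance day-specific (again assumed values):

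| Block SD (logit) | Subject only | Plus session | Plus session and block |
|---|---|---|---|
| 0 | 5% | 5% | 5% |
| 0.25 | 5.3% | 5.4% | 4% |
| 0.3 | 8% | 8% | 6% |
| 0.5 | 14% | 14% | 5% |
| 0.75 | 18% | 19% | 4% |

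With omission at 35% and 10% in the two conditions, as in 12.1, and no interaction, the subject-only rates at SD 0.3, 0.5 and 0.75 were 5.5%, 9.4% and 15%. Most cells had 300 runs, so Monte Carlo error is about 1 to 2 points; in the 35%/10% cells 9 to 19 of 300 fits failed and were left out.

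**Adding a session effect.** In a linear simulation with trial variance 1, session variance 0.1 and day-specific block variance 0.05, type I error rose from 12.7% (subject only) to 13.7% (subject and session), because session variance leaves the residual while the interaction's true variance stays the same. Adding a block-within-session effect brought it to 4.8%.

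**The case against.** Four objections deserve an answer.

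**A reader might infer that both models are wrong as written.** The documents do not support that. Only omission error is specified as 0/1 data. Section 12.1 powers reaction time on condition means within a person. If block or condition means are entered, block variance is already in the residual and this mechanism does not arise. This objection stands: the reaction-time half is conditional on the unit of analysis.

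**A reader might infer that the test is certainly inflated, by 8 to 17%.** No block variance or intraclass correlation appears anywhere in the documents. Rule and emotion pair are features of the task, and 6.2 has day 2 follow the day 1 procedure, so part of the block variance may repeat and cancel. The 8 to 17% is the extreme with no repetition. At full repetition the subject-only test is, if anything, slightly conservative. This stands too, but nothing in the documents shows that momentary attention or rule confusion would repeat a week later.

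**The interaction does not rest on a handful of blocks.** There are 25 × 2 × 5 = 250 blocks per group. That is correct, but replication across subjects does not repair a standard error that ignores block variance: R above does not depend on the number of subjects.

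**The obvious repair can overshoot.** A block-within-session term alone gave 0.9 to 1.9% type I error in linear simulations where repeating block effects were present but not modelled. This stands and shapes the fix.

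**Conclusion.** The concern holds in a conditional form. The omission-error model in 12.2, and the reaction-time model if fitted to single trials, assumes without saying so that no block-level or subject-by-treatment-by-valence variance differs between a subject's two sessions. Where such variance exists, the interaction's standard error is too small, and a session random effect does not correct it. The size ranges from nothing, when block effects are small or repeat, to a type I error of about three times nominal at the upper end of the assumed values. Those values are illustrations, since the documents supply none. The plan should be changed because the error falls on the test closest to the stated hypothesis and the remedy needs no data. The point does not bear on the sample size in 12.1.

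**What to change.** In 12.2:

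1. State the unit of analysis for reaction time.
2. Test the interaction in each group with one difference-of-differences per subject (nicotine minus placebo in emotional blocks, minus the same in non-emotional blocks) by a one-sample t-test with that group's completers minus 1 degrees of freedom (24 for 25 completers).
3. Alternatively, keep the mixed models and add random intercepts for subject-by-treatment-by-valence and for block within session, plus subject-by-block if block effects repeat across days.

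The cost is a short change of text and a wider interval for the interaction; no new data or participants are needed. For omission error, the contrast on raw rates estimates a risk difference rather than a log-odds ratio, so 12.2 should say which scale is meant.

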#### 5.4 Randomization

Treatment order will be block randomized by a member of the Center for Cognitive Medicine within the Department of Psychiatry at VUMC who is not otherwise involved in this study. All investigators and subjects will be blinded to treatment order.

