subject qualifies for the study and gives informed consent, the subject will be scheduled to return for day 1 of the study.

In some instances, the screening visit will be combined with the first testing session. This is to reduce the logistical burden for subjects for whom transportation may be difficult, as well as for individuals who may have difficulty getting time off from work. It is anticipated that this will reduce the number of subjects who drop out from the study without compromising subject safety.

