## 7.4 Justification for the use of placebo

The study is a crossover trial whereby all participants will receive one dose of nicotine and all participants will receive one dose of placebo. As this study is not designed to treat symptoms for a clinical benefit, we anticipate no potential harm that may come to the participant as a result of receiving placebo. Subjects will continue on their outpatient medications during this study.

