#### 8.1.2 Psychological assessments and Emotional Go/NoGo task

At screening, subjects will undergo non-invasive psychological assessment of a structured nature that has been consistently used without adverse effects in previous studies with a similar subject population. On testing days, subjects will perform the Emotional Go/NoGo task to measure impulsivity in an emotional context, a behavioral construct related to impulsive aggression. This task has been administered to healthy controls as well as patients with schizophrenia without report of adverse events. There is the potential risk that subjects may become fatigued during the performance of screening assessments or behavioral tasks, and that discussion of personal issues with study personnel in the context of screening issues may be stressful or uncomfortable. Because subjects participating in this study will be stable outpatients, it is unlikely that the stress posed by such measures will exacerbate baseline psychiatric symptoms.

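### The two-day crossover models leave out test day, so any day 1 to day 2 shift leaks into the nicotine main effect when the treatment orders are uneven

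*Combined protocol and SAP*

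**What the plan says.** Section 7.4 states the design: "The study is a crossover trial whereby all participants will receive one dose of nicotine", with one dose of placebo as well. Section 5.4 says "Treatment order will be block randomized" and gives neither a block size nor stratification by diagnostic group. Section 6.2 places the sessions about a week apart, never fewer than 5 days, and says of day 2: "The remainder of the procedure will be identical to day 1".

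Section 12.2 specifies a non-linear mixed model for omission error and a linear mixed model for reaction time. Each has a random subject effect, treatment as the main predictor, and "an independent adjustment variable block valence (emotional vs. non-emotional task), and the interaction of the latter two predictors". That is the whole list. No section adds test day, visit or treatment order.

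Section 12.2 predicts fewer errors under nicotine in the control blocks, and a larger gain in the negative-valence blocks. On numbers, section 12.1 says "We thus anticipate needing to enroll 30 subjects to result in 25 completers" and "We will match this group with a healthy control sample of similar size". Section 12.2 does not say whether the models are fitted to patients alone or to both groups together.

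**The concern.** Randomising the order makes a day effect cancel on average over repetitions of the trial. It does not remove the effect from the one trial that is run, unless the completers happen to split evenly between orders. Section 9.2 says that only subjects who complete both sessions give useful primary data, so dropout can unbalance even perfectly balanced blocks.

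The protocol gives reasons why the days might differ. The same task is repeated. For some subjects day 1 is also longer: "In some instances, the screening visit will be combined with the first testing session" (section 6.1), and screening includes an interview, questionnaires and an intelligence test. Section 8.1.2 adds: "There is the potential risk that subjects may become fatigued during the performance of screening assessments or behavioral tasks".

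At stake are the treatment main effect and the predicted control-block improvement. The treatment-by-valence interaction is much safer, because both valences are tested on each day and a common shift cancels.

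**Working it through.** **The plan's own figure.** For a paired t-test with an effect of 0.6 SD of the difference (my reading of the 0.6) and two-sided alpha 0.05, power is 80.4% at n = 24 and 82.1% at n = 25. Then 25/(1 − 0.15) = 29.4, which rounds up to 30. The 25 completers and 30 enrolled in section 12.1 reproduce.

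**The formula.** Let the true nicotine effect be τ and the day 2 minus day 1 shift be π. The nicotine-minus-placebo difference has mean τ + π in subjects given nicotine on day 2 and τ − π in the others. With n1 and n2 completers in the two orders, the unadjusted estimate has mean τ + πf, where f = (n1 − n2)/N. With a day term the bias from an additive shift is zero, and the standard error (SE) is multiplied by 1/√(1 − f²).

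**Likely splits.** Assume 30 patients randomised 15/15 and five lost regardless of order. The chance that k are lost from one order is C(15,k)·C(15,5−k)/C(30,5).

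| Split | Probability | Bias as share of day effect | SE ratio, valence-averaged effect | Paired-test power with day term, no day effect |
|---|---|---|---|---|
| 13/12 | 0.670 | 4% | 1.0008 | 81.9% |
| 14/11 | 0.287 | 12% | 1.0073 | 81.4% |
| 15/10 | 0.042 | 20% | 1.0206 | 80.4% |

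Mean share: 0.670 × 4% + 0.287 × 12% + 0.042 × 20% = 7.0%. Without the day term and with no day effect, power is 82.1%.

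If both groups are pooled (assumed 60 enrolled 30/30, ten lost), an even split has a 27% chance, 26/24 (4%) has 43%, 27/23 (8%) has 22%, and 12% or more has 8%. The mean share is 4.5%.

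**Check in the planned linear model.** Section 6.2 gives 3 emotional and 2 non-emotional blocks of 32 trials, half of them go trials: 48 + 32 = 80 per session. Generalised least squares in the random-intercept model gives a bias of 0.04, 0.12 and 0.20 per unit of day effect for treatment, and 0.000 for the interaction. With a day term, the control-block SE rises by 0.03%, 0.3% and 0.8% at the three splits (assumed subject SD 1, trial SD 2.5), and the interaction SE does not change.

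**Against the planned reaction-time effect.** Section 12.1 gives no correlation for reaction time, so 0.4, 0.6 and 0.8 are assumed. The planned effect is 0.6 × √(2(1 − r)) = 0.66, 0.54 or 0.38 SD.

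- Assumed day effect 0.3 SD: bias is 2–3% of the planned effect at 13/12 and 9–16% at 15/10.
- Assumed day effect 0.8 SD: 5–8% at 13/12 and 24–42% at 15/10.

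**Against the planned omission-error effect.** Moving from 35% to 10% is logit(0.35) − logit(0.10) = −0.619 + 2.197 = 1.578 on the log-odds scale. Assumed day effects of 0.3, 0.5 and 0.8 give at most 0.8%, 1.3% and 2.0% of that at 13/12, and 3.8%, 6.3% and 10% at 15/10. These are upper bounds, because the subject-specific effect exceeds the population one. In a simulated logistic random-intercept model with no drug effect and a day effect of 0.5 (assumed intercept −1.5, subject SD 0.8), the spurious nicotine effect at 15/10 was 0.101, against 0.20 × 0.5 = 0.10 expected. Adding test day brought it within 0.006 of zero.

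**The case against.** The strongest reply is that little is at risk. Section 2 frames the hypothesis as negative against neutral cues, which is the interaction, and a common day shift does not bias it. The error in the main effect has no systematic direction. Every absolute size rests on an assumed day effect. All of that stands, and it limits the weight of the point. Section 12.1 nevertheless sizes the study on a difference between conditions, so the main effect is not incidental.

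The uneven split depends on exactly 25 completers. With four dropouts from 15/15, 26 complete. The chance of exact balance is then 40%, of 14/12 50% and of 15/11 10%, with a mean share of 5.4%. That is correct; the expected bias is of the same order. The 24–42% figures combine a split with a 4% chance and a large assumed shift, so they mark an extreme.

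It can also be said that the omission makes the paired test conservative. In simulation with five random dropouts and no drug effect, its type I error fell from 5.0% to 4.0%, 3.2% and 1.3% at shifts of 0.335, 0.5 and 0.9 SD of the difference, because the shift enters the variance. That is a cost too: under balance, power at n = 25 falls to about 79% for a shift of 0.3 SD and 69% for 0.6 SD. Nor does it carry over to section 12.2, whose models are not the paired test. In a trial-level within-subject linear model (assumed trial SD 2.5, no subject-by-session variance), omitting day raised type I error to about 8–20% at 14/11 and 12–49% at 15/10 for shifts of 0.3–0.8. Adding day restored about 5%.

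Finally, evidence for a day effect is thin. Section 8.1.2 is a statement of participant risk, and combined visits occur only sometimes. This is fair, but the term costs so little that it does not need strong evidence.

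**Conclusion.** The concern holds. The omission and the formula are certain: the models have no test-day term, and an average day shift enters the nicotine main effect and the control-block contrast in proportion to the order imbalance. For patients alone the share is most likely 4%, sometimes 12%, rarely 20%. This assumes 15/15 randomisation and five dropouts unrelated to order. Pooled with controls it averages 4.5% and may be zero.

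The size of the day shift is not in the documents, so the absolute harm cannot be stated; it is probably small. This is avoidable error given the realised split, not a systematic lean. The change is worth making because it is nearly free, not because the omission threatens the main hypothesis.

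**What to change.** Add test day (1 or 2) as a fixed effect in both the omission-error model and the reaction-time model in section 12.2. Add test day by group only in a model that also contains diagnostic group. A table of completers by treatment order would let readers see the imbalance, though that is a matter of reporting.

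The cost is one degree of freedom per model and a line of text, with no new data. Precision and power costs are those tabulated above: at most 2.1% on the SE and 1.7 percentage points of paired-test power at 15/10.

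The term removes only an average, additive shift. It does not remove carryover, a shift that differs by valence, or chance imbalance between orders in who had a combined screening and testing visit.
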